### 3.2 Primary Study Endpoints

(1) To assess the role of neurogenic inflammation in symptomatic scarring alopecia and (2) assess the efficacy of topical 6% gabapentin in the management of symptomatic scarring alopecia patients. Subjects' disease burden will be assessed by clinical exam, qualitatively with surveys and neurometer study, and skin biopsies to confirm disease diagnosis, assess disease inflammation, and measure CGRP levels. Subjects will begin topical 6% gabapentin treatment for 12 weeks starting at Visit 2. They will be followed up every 4 weeks during treatment and will be reassessed at week 12 (visit 5) with clinical exam, qualitatively with surveys and neurometer study, and final biopsies to evaluate the impact of gabapentin on the disease and CGRP levels. The surveys to be filled out by the subjects include the Dermatology Life Quality Index (DLQI), Short Form (36) Health Survey (SF-36), Visual Analog Scale for Pain, and Visual Analog Scale for Itch.

CONFIDENTIAL

This material is the property of the University of Minnesota. Do not disclose or use except as authorized in writing by the study sponsor

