## 7 Statistical Plan

### 7.1 *Sample Size Determination*

This is a pilot study with the plan to enroll 10 subjects. The reasoning for sample size selection is to proceed with preliminary studies in a small group. All subjects will be selected based on inclusion and exclusion criteria.

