### 7.2 *Statistical Methods*

An intent-to-treat analysis will be performed in all subjects for symptoms and sign scores comparing the last treatment visit to baseline. A combination of methods will be included for analysis. Descriptive statistics including either numerically or graphical representations to summarize the data will be used.

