**RAND 36-Item Health Survey 1.0 Questionnaire Items**

1. In general, would you say your health is:
  - 1 Excellent
  - 2 Very Good
  - 3 Good
  - 4 Fair
  - 5 Poor
  
2. **Compared to one year ago**, how would you rate your health in general **now**?
  - 1 Much better now than one year ago
  - 2 Somewhat better now than one year ago
  - 3 About the same
  - 4 Somewhat worse now than one year ago
  - 5 Much worse now than one year ago

The following items are about activities you might do during a typical day. Does **your health now limit you** in these activities? If so, how much?

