**(Check one number on each line)**

	Yes, Limited a Lot ▼	Yes, Limited a Little ▼	No, Not limited at All ▼
3. Vigorous activities , such as running, lifting heavy objects, participating in strenuous sports	 1	 2	 3
4. Moderate activities , such as moving a table, pushing a vacuum cleaner, bowling, or playing golf	 1	 2	 3
5. Lifting or carrying groceries	 1	 2	 3
6. Climbing several flights of stairs	 1	 2	 3
7. Climbing one flight of stairs	 1	 2	 3
8. Bending, kneeling, or stooping	 1	 2	 3
9. Walking more than a mile	 1	 2	 3
10. Walking several blocks	 1	 2	 3
11. Walking one block	 1	 2	 3
12. Bathing or dressing yourself	 1	 2	 3

CONFIDENTIAL

During the **past 4 weeks**, have you had any of the following problems with your work or other regular daily activities **as a result of your physical health?**

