**(Check One Number on Each Line)**

	Yes ▼	No ▼
17. Cut down the amount of time you spent on work or other activities	 1	 2
18. Accomplished less than you would like	 1	 2
19. Didn't do work or other activities as carefully as usual	 1	 2
20. During the past 4 weeks , to what extent has your physical health or emotional problems interfered with your normal social activities with family, friends, neighbors, or groups?		
(Check One Number)		
 1 Not at all		
 2 Slightly		
 3 Moderately		
 4 Quite a bit		
 5 Extremely		

CONFIDENTIAL

21. How much **bodily** pain have you had during the **past 4 weeks**?

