**(Check One Number on Each Line)**

	All of the Time ▼	Most of the Time ▼	A Good Bit of the Time ▼	Some of the Time ▼	A Little of the Time ▼	None of the Time ▼
23. Did you feel full of pep?	 1	 2	 3	 4	 5	 6
24. Have you been a very nervous person?	 1	 2	 3	 4	 5	 6
25. Have you felt so down in the dumps that nothing could cheer you up?	 1	 2	 3	 4	 5	 6
26. Have you felt calm and peaceful?	 1	 2	 3	 4	 5	 6

CONFIDENTIAL

27. Did you have a lot of energy? 1    2    3    4    5    6
28. Have you felt downhearted and blue? 1    2    3    4    5    6
29. Did you feel worn out? 1    2    3    4    5    6
30. Have you been a happy person? 1    2    3    4    5    6
31. Did you feel tired? 1    2    3    4    5    6

32. During the **past 4 weeks**, how much of the time has your **physical health or emotional problems** interfered with your social activities (like visiting with friends, relatives, etc.)?

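### SF-36 item 21 in Appendix B gives 'Severe' and 'Very severe' bodily pain the same code, so a change between them is recorded as no change

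*Protocol*

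**What the plan says.** Section 3.2 assesses disease burden partly through surveys: "The surveys to be filled out by the subjects include the Dermatology Life Quality Index (DLQI), Short Form (36) Health Survey (SF-36", with visual analogue scales for pain and itch completing the set. Footnote a to Table 1 repeats the same four instruments. None of them is singled out as primary.

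Appendix B reproduces the SF-36 form, identified there as the RAND 36-item survey, version 1.0. Item 21 reads "21. How much bodily pain have you had during the past 4 weeks". Its six answers and printed codes are: None 1, Very mild 2, Mild 3, Moderate 4, Severe 5, Very severe 5.

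The form's other six-level items are 23 to 31, which include "23. Did you feel full of pep" and "24. Have you been a very nervous person". These are coded 1 to 6, one code per answer.

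Section 7.2 sets the comparison: "An intent-to-treat analysis will be performed in all subjects for symptoms and sign scores comparing the last treatment visit to baseline". Section 7.1 gives the size of the study: "This is a pilot study with the plan to enroll 10 subjects". Section 9.2 lists the surveys as source data and allows data to be transcribed to case report forms or entered directly into an electronic system.

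**The concern.** A data collection form should let the recorded number identify the answer. Here two differently worded answers map to the same number, at the severe end of a pain item, in a trial whose subjects are enrolled because they have symptoms.

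A subject who goes from very severe to severe bodily pain would be recorded as unchanged. So would one who worsens from severe to very severe. A change between *Very severe* and any milder answer would be understated by one code. Section 9.2 permits entry straight into an electronic system, so if only the printed code is keyed, the distinction disappears from the dataset even though it survives on paper.

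The error lies in the form attached to the protocol. A statistical analysis plan would not normally be the place where it is caught.

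**Working it through.** The protocol states no figure for this item, so there is none to reproduce. The check compares the printed codes with what six distinct codes would give.

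**Inputs (Appendix B)**
- Item 21: six answers, codes 1, 2, 3, 4, 5, 5, a high code meaning worse.
- Items 23 to 31: six answers, codes 1, 2, 3, 4, 5, 6.
- Number of subjects: 10 (Section 7.1).

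**Step 1: change in code.**
- *Very severe* to *Severe*: as printed, 5 − 5 = 0; with distinct codes, 6 − 5 = 1.
- *Very severe* to *Moderate*: as printed, 5 − 4 = 1; with distinct codes, 6 − 4 = 2.
- Changes among the five milder answers, *None* to *Severe*, are the same either way.

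**Step 2: size on a 0 to 100 item scale.** The protocol gives no scoring key, so even spacing with 100 as best is an assumption. The score is 100 × (m − code)/(m − 1), where m is the number of levels the key assumes.

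| Answer | Distinct codes, m = 6 | Printed codes, six-level key | Printed codes, five-level key |
|---|---|---|---|
| None | 100 | 100 | 100 |
| Very mild | 80 | 80 | 75 |
| Mild | 60 | 60 | 50 |
| Moderate | 40 | 40 | 25 |
| Severe | 20 | 20 | 0 |
| Very severe | 0 | 20 | 0 |

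With distinct codes the top step is 20 − 0 = 20 points. With the printed codes it is 20 − 20 = 0 or 0 − 0 = 0, depending on the key. Under a six-level key only *Very severe* is misplaced, by 20 points. A five-level key would misplace *Severe* by 20 and also shift the middle answers (for example *Moderate*, 25 instead of 40), but nothing in the protocol calls for such a key.

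**Step 3: effect on a group mean.** If k of the 10 subjects move from *Very severe* to *Severe*, the mean item change is understated by 20k/10 = 2k points: 0 if nobody does, 2 if one does, and 20 in the extreme case where all ten do. The protocol gives no expected distribution of answers, so k is unknown.

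**The case against.** Several points on the other side are sound.

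- **The digit may be misread.** It is a small subscript, and a misreading in the PDF text cannot be fully excluded. Against that, the sixes in items 23 to 31 and the 1-to-5 codes of items 20 and 22 read correctly. The original form should settle it.
- **The answer is recoverable.** The two options are worded separately, and Section 9.2 makes the surveys source data, so the ticked box shows which was meant. This makes the error repairable, but the form is still wrong.
- **The reach is small.** Item 21 asks about bodily pain, not scalp pain. Pain is also captured by the Pain VAS (Appendix D), LPPAI item B (Appendix E) and, together with other sensations, DLQI question 1 (Appendix A). Section 7.2 promises descriptive summaries and names no test or threshold that turns on this item.

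A reader might go further and infer that the single RAND-36 score line closing Appendix B is also wrong, because the items run in opposite directions. They do. On "In general, would you say your health is" a high code is worse, whereas in items 3 to 12 the highest code is "No, Not limited at All". In all, high is better on 25 items and worse on 11. A plain sum of printed codes would give 100 for perfect health and 84 for the worst.

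The documents do not support that conclusion. The form prints a blank and no instruction to add. Where the protocol wants a sum or formula it prints one, as for the DLQI and the LPPAI. The instrument is named, and reversal and scale construction are commonly left to an analysis plan, which is not at hand. The total is undefined here, not wrong.

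**Conclusion.** The point stands in a narrow form: item 21 has six answers and five distinct codes, which departs from the form's own practice for six-level items. Entered as printed, a change between *Severe* and *Very severe* is recorded as zero. The loss is one code, or 20 points on the item if six levels are evenly spaced on 0 to 100. That spacing is an assumption, and the finding also assumes that the printed digit is as read and that data are keyed from the printed code.

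The consequence is limited to this SF-36 item and to subjects who tick one of its two worst answers. It would be a mistake to infer that the trial's pain result as a whole is wrong. The SF-36 is one of four surveys with none designated primary, and the Pain VAS and LPPAI pain item are unaffected. Nor do the documents give grounds for making items 21 and 22 the SF-36 symptom result, since no such scale is designated. This is a minor correction, worth making because it is cheap and because one misrecorded change is a tenth of a 10-subject sample.

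**What to change.** 1. Check the code beside *Very severe* in item 21 against the original form. If it is already 6 there, nothing more is needed.
2. If it is 5, reprint the page with codes 1 to 6 for the six answers and carry the same codes into the case report form or database.
3. For any forms already completed, re-enter item 21 from the box ticked, not from the printed number.

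The cost is one corrected form page and, at most, one item to re-key on each completed survey. No new data, visits or subjects are required.

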### **3.3 Secondary Study Endpoints**

To assess the safety, tolerability, and efficacy of topical gabapentin for 12 weeks in subjects with lymphocytic-type symptomatic scarring alopecia. Subjects will be followed up 4, 8, and 12 weeks during treatment with topical 6% gabapentin starting day 0 (Visit 2) and ending week 12 (Visit 5). Medication side effects, blood levels, and adverse experiences will be recorded.

### **3.4 Primary Safety Endpoints**

A primary safety endpoint will take place when the first 5 subjects complete the study.

## **4 Subject Selection and Withdrawal**

### **4.1 Inclusion Criteria**

1. Male and female adults, greater than 18 years of age
2. Biopsy-proven diagnosis of primary scarring alopecia of lymphocytic inflammatory infiltrate type, indicated as one of the following conditions: lichen planopilaris, frontal fibrosing alopecia, or central centrifugal cicatricial alopecia
3. At least one persistent scalp symptom associated with inflammation: pain, burning, itch, tingling/crawling, stinging, or tenderness
4. Able to complete survey and questionnaire subjectively
5. Consents to participate in neurometer study and scalp biopsy acquisition
6. Willingness to adhere to study protocol
7. If subject is taking a neuromodulatory medication (including capsaicin cream, tricyclic antidepressants, carbamazepine, phenytoin, topiramate, oxcarbazepine, lamotrigine, morphine, Botox, etc), he or she must be a stable dose for at least 6 months prior to study enrollment

The gender of the subjects will not determine enrollment. There is no requirement of male to female ratio for this study. The age range of the subjects will be 18 years and older. No specific racial or ethnic restrictions will be present for this study. The FDA lists gabapentin as Pregnancy Category C: studies in animals have shown some harm to the fetus but its effects on human fetus are unknown due to limited data. It has not been found to be harmful during breastfeeding. Therefore, female subjects of childbearing potential will not be excluded since the drug will be topically administered with minimal systemic absorption.

### **4.2 Exclusion Criteria**

1. Allergy or intolerance to gabapentin or the substances used in its compounding
2. Underlying disease that might be adversely affected by topical gabapentin
3. Application of topical immunomodulatory or immunosuppressive agent to the scalp in the preceding 2 weeks
4. Systemic administration of corticosteroid or other systemic treatment (i.e., methotrexate, phototherapy) that has immunomodulatory or other immunosuppressive mechanism of action, in the preceding 8 weeks

CONFIDENTIAL

5. Clinical evidence of secondary skin infection
6. Individuals who have undergone scalp reduction surgery or hair transplantation
7. Asymptomatic disease
8. Immunosuppression due to disease state or use of systemic/topical biological agents (HIV, chemotherapy, immunomodulators, history of transplantation)
9. Any Investigational medications within the past 30 days, including those for migraines or scarring alopecias (anti-CGRP agents)
10. Use of GABAergic medications (including gabapentin and pregabalin) in the preceding 2 months
11. Use of illicit drugs or opioid medications
12. Evidence of anemia, thyroid disease, sarcoidosis or other medical condition that could impact hair growth and adversely impact the outcome of the study
13. Implantable Cardioverter Defibrillator (ICD) or pacemaker
14. Subject has any medical condition that, in the judgment of the Investigator, would jeopardize the subject's safety following exposure to the administered medications

If subjects are taking medications/treatments for their scarring alopecia at baseline visit, they will be asked to stop taking/administering them as described in the exclusion criteria.

### **4.3 Subject Recruitment and Screening**

Subjects will be identified by the Principal Investigator, [name]. The study coordinator will assist in describing the study and answering questions.

Advertisements may be posted on the University of Minnesota campus and surrounding community. Advertising will be submitted to the Institutional Review Board (IRB) for approval before it is used. Language will also be submitted to the IRB so information about the study can be posted on our department website, as well distributed to the Cicatricial Alopecia Research Foundation.

In the screening process (Visit 1), subjects will be evaluated using the inclusion and exclusion criteria.

### **4.4 Early Withdrawal of Subjects**

#### **4.4.1 When and How to Withdraw Subjects**

Participation in this study is voluntary. Subjects are free to withdraw at any time. Once initiated, individual subjects will receive enough gabapentin for 4 weeks at a time to administer. If withdrawn, subject will be asked to terminate use of the investigational drug and return the remaining gabapentin solution.

CONFIDENTIAL

This material is the property of the University of Minnesota. Do not disclose or use except as authorized in writing by the study sponsor

Investigators may withdraw subjects from the study if subjects fail to adhere to the study protocol requirements (e.g. use of other topical, oral or other medical treatments used for management of scarring alopecia during the study). Subjects may also be withdrawn if they experience an adverse reaction to the study medication or if their gabapentin blood levels exceed safety levels (>16 ug/mL).

#### **4.4.2 Data Collection and Follow-up for Withdrawn Subjects**

Data collection of withdrawn subjects will be collected up to the point of withdrawal. This data will still be included in the pool-data of the study for further analysis. Subjects who withdraw from further data collection will not be replaced with additional subjects.

If a subject withdraws consent to participate in the study, attempts will be made to obtain permission to record data up to the protocol-described end of subject follow-up period.

Three phone calls one week apart one from another will be made to the subjects lost to follow-up to record data up to the protocol-described end of subject follow-up period.

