## **3 Study Design**

### **3.1 General Design**

This is a cohort study.

Every subject is expected to schedule 6 visits total to complete the study. The total duration of the study for each volunteer is expected to be approximately 14 weeks.

Prior to gabapentin treatment, there is one visit to screen individuals for participation in the study and to obtain consent. After consent is signed, this visit will also include obtaining history from the subject, clinical evaluation, survey completion, neurometer study, photography, and scalp biopsies. At this initial visit, a total of four 4-mm skin biopsies will be collected. Two biopsies will be collected from affected, symptomatic scalp, and two skin biopsies will be collected from clinically unaffected scalp. Routine histology, confocal microscopy examination, and, if indicated, ELISA CGRP level analysis will be performed on the biopsy specimens. Subjects will start topical 6% gabapentin treatment on Visit 2 (Day 0). Four remaining visits will be scheduled to follow subjects after the start of topical 6% gabapentin treatment. Visits 3, 4 and 5 will occur 4, 8 and 12 weeks respectively after treatment with gabapentin is started. These visits will include labwork to check gabapentin blood levels. During Visit 5, the subject will also be reassessed through clinical evaluation, completion of surveys, neurometer study, photography, and four 4-mm scalp biopsies. Visit 6 will be a follow-up visit two weeks after completion of treatment for suture removal and clinical evaluation of the subject.

CONFIDENTIAL

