### ***Adverse Event Reporting Period***

The study period during which adverse events must be reported is normally defined as the period from the initiation of any study procedures to the end of the study treatment follow-up. For this study, the study treatment follow-up is defined as 14 weeks following the start of administration of study treatment (Day 0).

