### ***Abnormal Laboratory Values***

Gabapentin blood levels will be monitored to ensure gabapentin toxicity does not occur. If gabapentin levels reach or exceed 16 ug/mL, gabapentin treatment will be interrupted. Abnormal gabapentin levels will be recorded as an adverse event and followed by the investigator until the event has resolved.

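### Sections 4.4.2 and 7.3 end data collection at withdrawal, but 8.1 and 8.2 record adverse events to Week 14; for investigator-withdrawn subjects the two must be reconciled

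*Protocol*

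**What the plan says.** **Cut-off at withdrawal.** Section 4.4.2 states: "Data collection of withdrawn subjects will be collected up to the point of withdrawal". Section 7.3 repeats the sentence for the analysis population. Data gathered before withdrawal stay in the pooled data.

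**Two groups with a provision beyond the cut-off.** Section 4.4.2 asks sites to seek permission from subjects who withdraw consent, and to make three phone calls to subjects lost to follow-up. In both cases the aim is data to the end of the follow-up period.

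**Who can be withdrawn by the investigator.** Section 4.4.1 gives two kinds of ground. One is conduct: "Investigators may withdraw subjects from the study if subjects fail to adhere to the study protocol requirements". The other is safety: "Subjects may also be withdrawn if they experience an adverse reaction to the study medication or if their gabapentin blood levels exceed safety levels".

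**Adverse-event window.** Section 8.1 (Adverse Event Reporting Period) says that "the study treatment follow-up is defined as 14 weeks following the start of administration of study treatment (Day 0". Section 8.2 has all adverse events in the study period recorded. Neither section exempts withdrawn subjects.

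**Follow-up of events already known.** Section 8.1 (Post-study Adverse Event) and section 8.2 have events followed until they resolve or are otherwise accounted for. On blood levels, section 8.1 says: "Abnormal gabapentin levels will be recorded as an adverse event and followed by the investigator until the event has resolved".

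**The concern.** Take a subject whom the investigator withdraws at Week 4 and who has a new adverse event at Week 7. Sections 4.4.2 and 7.3 say that data collection has ended. Sections 8.1 and 8.2 say that the event falls inside the reporting period and must be recorded. The protocol does not say which rule governs.

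The gap is uneven. Subjects who withdraw consent and subjects who cannot be reached have a stated route to data at the end of follow-up. Subjects withdrawn by the investigator, who may be both willing and reachable, have none. Section 6 and Table 1 contain no early-termination visit. The section 8.1 instruction to report later events is given at the last scheduled visit, which a withdrawn subject may never attend.

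The protocol also does not cleanly separate stopping drug from leaving the study. Section 4.4.1 treats an adverse reaction or a high level as a possible ground for withdrawal. For a high level, section 8.1 speaks of interrupting treatment and section 8.5 of terminating it. Whether the cut-off applies can therefore depend on the label that the investigator chooses.

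Safety is part of the secondary objective (section 2) and a secondary endpoint (section 3.3). An adverse event that was never collected cannot be recovered at analysis.

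**Working it through.** **1. Reproduce the 14-week window.** Section 3.2 gives the treatment length: "Subjects will begin topical 6% gabapentin treatment for 12 weeks starting at Visit 2". Section 3.1 gives the follow-up: "Visit 6 will be a follow-up visit two weeks after completion of treatment". So 12 + 2 = 14 weeks from Day 0, which agrees with section 8.1 and with Visit 6 at Week 14 in Table 1.

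**2. Part of the window left open if 4.4.2 is followed.** For withdrawal at week w, the uncovered time is 14 − w, as a share (14 − w)/14.

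| Withdrawal at | Weeks uncovered | Share of the 14 weeks |
|---|---|---|
| Week 4 | 14 − 4 = 10 | 10/14 = 71% |
| Week 8 | 14 − 8 = 6 | 6/14 = 43% |
| Week 12 | 14 − 12 = 2 | 2/14 = 14% |

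If collection ran to Week 14 for every withdrawn subject, the uncovered time would be 0.

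**3. What is and is not lost in those weeks.**

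| Item after an investigator-initiated withdrawal | 4.4.2 and 7.3 | 8.1 and 8.2 |
|---|---|---|
| Course of the event or level that led to withdrawal | Ends | Followed to resolution or explanation |
| New adverse event before Week 14 | Ends | Recorded |
| Scheduled assessments (surveys, LPPAI) | Ends | Not addressed |
| Possibly related serious event after the study period | Not addressed | Recorded and reported (8.2) |

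The specific follow-up rules protect the first and last rows. The real exposure is the second and third rows.

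**4. How often this might arise (illustration only).** Section 1.5 cites a vulvodynia cohort in which 8% stopped use because of irritation. Assume that the rate carries over to the scalp, and that each such subject is also withdrawn from the study. With 10 subjects:

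- expected number: 10 × 0.08 = 0.8;
- chance of at least one: 1 − 0.92^10 = 57%;
- at half the rate (4%): 1 − 0.96^10 = 34%;
- at twice the rate (16%): 1 − 0.84^10 = 83%.

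Withdrawal for non-adherence is not counted here, and the protocol gives no rate for it.

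**The case against.** The strongest reply is that section 8 is the specific text on adverse events, while 4.4.2 and 7.3 are general rules on study data and the analysis pool. Read that way, a site records adverse events to Week 14 and ends everything else at withdrawal, so the two can be reconciled. It is therefore too strong to say that a site cannot comply with both. But the protocol does not state this precedence, and 4.4.2 names exceptions for two groups and none for this one. The ambiguity stands.

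A reader might infer that subjects withdrawn for an adverse reaction or a high level get the shortest safety follow-up. The documents do not support that. The event or level is followed to resolution, possibly beyond Week 14. Subjects withdrawn for non-adherence face the same cut-off and may have no open event to follow.

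A reader might also infer that the safety summary is made to look more favourable. The event that led to withdrawal is recorded and followed, and nothing in the protocol allows a bias to be sized. What could be missed is later, new events.

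Two further points stand. Withdrawal on these grounds is discretionary, and a subject who only stops drug is not clearly under the cut-off. The 8% concerns stopping use in another condition, not withdrawal from this study.

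**Conclusion.** The conflict is real but limited in scope. For investigator-withdrawn subjects, whatever the ground, the protocol gives two incompatible instructions on new adverse events between withdrawal and Week 14, and no route to later scheduled assessments. Following 4.4.2 leaves 10 of 14 weeks uncovered for withdrawal at Week 4, and 6 of 14 at Week 8. These figures assume that 4.4.2 governs. They apply to new events and assessments only, not to the event or level behind the withdrawal.

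The number affected is unknown. The 57% chance of at least one in 10 (34% to 83% for rates of 4% to 16%) rests on a rate borrowed from another condition and is no forecast.

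With 10 subjects, and no replacement of those who withdraw from further data collection (4.4.2), one truncated record is 1/10 = 10% of the safety data. This should be settled in the protocol, because it decides what is collected.

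**What to change.** Reconcile 4.4.1, 4.4.2 and 7.3 with 8.1, 8.2 and 8.5:

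- Define stopping study drug and stopping data collection as separate events, and use the terms consistently in all six sections.
- State that for a subject whom the investigator withdraws, on any ground, adverse-event collection by visit or phone continues to the Week 14 end already set in 8.1, unless the subject refuses.
- Keep the cut-off at withdrawal only for subjects who refuse further data collection, and word 7.3 to match.
- State that the follow-up of unresolved events and abnormal levels in 8.1 and 8.2 continues after withdrawal.
- Say which scheduled assessments, if any, are still sought. The Visit 5 biopsies and neurometer study need not be required of these subjects.

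This changes no dose, threshold or rule for stopping treatment. The cost is a protocol wording change and a few off-drug contacts, probably for very few subjects.
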